Document Date: June 23, 2022

Three Dimensional Assessment of Maxillary Molars Following Distalization Using Two Different Approaches

A Thesis
Submitted to Faculty of Dentistry
Ain-Shams University
In Partial Fulfillment of the Requirements of
Master's Degree in Orthodontics

Faculty of Dentistry
Ain Shams University
2022

Statistical analysis

Statistical analysis was performed with SPSS 20^{®*}, Graph Pad Prism^{®**}, and Microsoft Excel 2016^{***}.

All quantitative data were explored for normality by using Shapiro Wilk Normality test and presented as means and standard deviation (SD) values. All qualitative data were presented as frequency & percentage. All data were presented in (43) tables & (38) graphs.

Tests used:

- Comparisons 2 different groups was performed by using Mann Whitney test.
- Comparisons 2 successive follow ups periods was performed by using Paired t-test.
- Comparison between quantitative continuous data (Age & Duration) was performed by Independent t-test.
- Comparison between qualitative dichotomous data (Gender) was performed by Chi square test.
- Reliability test was performed by using Intra-class Correlation Coefficient (ICC).

* Statistical Package for Social Science, IBM, Armonk, NY, USA.

** Graph Pad Technologies, San Diego, CA, USA

*** Microsoft Co-operation, Redmond, WA, USA.

* All results presented as:

I. Normality test.

II. Baseline characteristics:

- A. Age.
- B. Gender.
- C. Duration
- D. Pretreatment measurements. (Appendix IV).

III. Measurements

The following measurements were carried for both group I and group II as well as in comparison between the two groups.

A. Skeletal measurements

- 1. Skeletal antero-posterior measurements.
- 2. Skeletal vertical measurements.

B. Dental measurements

- 1. Angular
- 2. Linear

C. Soft tissue measurements.

IV. Reliability: (Appendix V)

- A. Inter-observer.
- B. Intra-observer.

I. Normality test:

Exploration of the given data was performed using Shapiro-Wilk test and Kolmogorov-Smirnov test for normality. As Listed in (Table 11) and showed in (Figure 53), it was revealed that the significant level (P-value) was shown to be insignificant as P-value > 0.05 , which indicated that alternative hypothesis was rejected, and the concluded data originated from normal distribution (parametric data) resembling normal Bell curve in pre & post measurements while P value was significant in the difference between both groups which indicated nonparametric data.

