Table (11): Normality exploration of both groups regarding all measurements:

Measurements		Group I Single Coil Spring	Group II Double Coil Spring
Skeletal.	Pre	> 0.05	> 0.05
	Post	> 0.05	> 0.05
	Difference	$< 0.05^*$	$< 0.05^*$
Dental	Pre	> 0.05	> 0.05
	Post	> 0.05	> 0.05
	Difference	$< 0.05^*$	$< 0.05^*$
Soft tissue	Pre	> 0.05	> 0.05
	Post	> 0.05	> 0.05
	Difference	$< 0.05^*$	$< 0.05^*$

* Significant difference as $P < 0.05$

[figure not shown]
[figure not shown]

Figure (53): Scattered chart represents normal bell curve of normality test.

II. Baseline characterized:

1. Age:

In group I, minimum age was (18.4), maximum was (21.2), while mean \pm standard deviation was (19.42 ± 1.03) . In group II, minimum age was (18.08), maximum was (23.17), while mean \pm standard deviation was (20.7 ± 2.24) , as presented in table (12) and figure (54).

Comparison between both groups was performed by using Independent t-test which revealed insignificant difference between them as $P > 0.05$, as presented in table (12).

Table (12): Minimum, maximum, mean & standard deviation of age in both groups:

	Min	Max	M	SD	P value
G I	18.4	21.2	19.42	1.03	0.09
G II	18.08	23.17	20.7	2.24	

N: count

Min: minimum

Max: maximum

M: mean

SD: standard deviation

[figure not shown]

Figure (54): Bar chart showing mean of age in both groups.

2. Gender:

In gender all companions were performed by using Chi square test. In group I, male (16.67%) was significantly lower than female (83.3%) as $P < 0.05$, while in group II male (33.3%) was insignificantly lower than female (66.6%) as $P > 0.05$, as presented in table (13) and figure (55).

Also, comparison between group I & II reveled insignificant difference between them in both male & female as $P > 0.05$ as presented in table (13).

Table (13): Frequency & percentage of gender distribution in both groups:

Group	Male		Female		P value
	N	%	N	%	
Group I	2	16.67%	10	83.33%	0.001*
Group II	3	33.33%	6	66.67%	0.13
P value	0.34		0.34		

N: count

%: percentage

P: probability level which is significant at $P \leq 0.05$

[figure not shown]

Figure (55): Bar chart showing percentage of gender distribution in both groups

3. Duration:

In group I, minimum duration was (5.5 months), maximum was (9.73 months), while mean \pm standard deviation was (8.03 ± 2.9) . In group II, minimum duration was (4 months), maximum was (14.9 months), while mean \pm standard deviation was (10.59 ± 3.89) .

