Figure (60): Bar chart showing mean of pretreatment, post treatment records and difference between them regarding vertical skeletal measurements in group I.

- **Group II:**

In group II pretreatment records, post treatment records and difference between them regarding vertical skeletal measurements were presented in table (19) and figure (61).

Comparison between pretreatment & post treatment records was performed by using Paired t-test which revealed insignificant difference between them in all measurements as $P > 0.05$, as presented in table (19).

Table (19): Mean & standard deviation of pretreatment, post treatment records and difference between them regarding vertical skeletal measurements in group II:

Group II Vertical Skeletal Measurements	Pre		Post		Difference		P value
	M	SD	M	SD	MD	SD	
PP-SN angle	9.47	3.58	9.64	3.31	0.17	0.27	0.54
ANS-Me distance	65.55	4.86	65.04	5.93	-0.52	1.66	0.376
MP-SN angle	36.99	3.05	36.55	2.81	-0.44	1.40	0.377

M: mean

SD: standard deviation

MD: mean difference

P: probability level which is significant at $P \leq 0.05$

[figure not shown]

Figure (61): Bar chart showing mean of pretreatment, post treatment records and difference between them regarding vertical skeletal measurements in group II.

- **Comparison between both groups:**

Comparison between group I & II regarding difference between pretreatment & posttreatment records of vertical skeletal measurements was performed by using Mann Whitney test which revealed insignificant difference between them regarding all measurements, as presented in table (20) and figure (62).

Table (20): Comparison between both groups regarding vertical skeletal measurements:

Difference Vertical Skeletal Measurements	Group I		Group II		P value
	MD	SD	MD	SD	
PP-SN angle	0.31	0.91	0.17	0.27	0.66
ANS-Me distance	0.04	1.43	-0.52	1.66	0.24
MP-SN angle	-0.15	0.61	-0.44	1.40	0.61

SD: standard deviation

MD: mean difference

P: probability level which is significant at $P \leq 0.05$

[figure not shown]

Figure (62): Bar chart showing comparison between both groups regarding vertical skeletal measurements.

B. Dental

1. Angular

a. Anteroposterior

• Group I:

In group I pretreatment records, post treatment records and difference between them regarding anteroposterior- angular- dental measurements were presented in table (21) and figure (63).

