Figure (64): Bar chart showing pretreatment, post treatment records and difference between them regarding anteroposterior angular dental measurements in group II.

- **Comparison between both groups:**

Comparison between group I & II regarding difference between pretreatment & posttreatment records of anteroposterior angular dental measurements was performed by using Mann Whitney test which revealed insignificant difference between them regarding all measurements except U6-FHP (Group I was significantly higher than group II) as $P < 0.05$, as presented in table (23) and figure (65).

Table (23): Comparison between both groups regarding anteroposterior angular dental measurements:

Difference Anteroposterior Angular Dental Measurements	Group I		Group II		P value
	MD	SD	MD	SD	
U1-NA	0.44	1.88	0.18	0.85	0.70
U1-FHP	0.97	1.46	0.43	0.83	0.33
U4-FHP	1.10	4.80	4.42	5.18	0.82
U5-FHP	5.06	6.02	6.25	5.34	0.61
U6-FHP	-4.72	9.69	-13.54	8.61	0.03*
U7-FHP	-4.87	8.16	-8.30	0.81	0.16

SD: standard deviation

MD: mean difference

P: probability level which is significant at $P \leq 0.05$

[figure not shown]

Figure (65): Bar chart showing comparison between both groups regarding anteroposterior angular dental measurements.

b. Rotation

- **Group I:**

In group I pretreatment records, post treatment records and difference between them regarding rotation- angular- dental measurements were presented in table (24) and figure (66).

Comparison between pretreatment & post treatment records was performed by using Paired t-test which revealed insignificant difference between them in all measurements as $P > 0.05$ except U5-MSP and U7-MSP as there was a statistical significant difference as $P < 0.05$ (Post was significantly higher than prerecord), while in U6-MSP there was a highly statistical significant difference as $P < 0.001$ (Post was significantly higher than prerecord) as presented in table (24).

Table (24): Mean & standard deviation of pretreatment, post treatment records and difference between them regarding rotation angular dental measurements in group I:

Group I Rotation Angular Dental Measurements	Pre			Post			P value
	M	SD	M	SD	MD	SD	
U4-MSP	71.89	6.73	74.95	6.62	3.06	8.70	0.248
U5-MSP	68.84	7.63	63.36	7.23	-5.48	4.79	0.002*
U6-MSP	32.38	6.45	50.50	10.29	18.12	8.35	0.000**
U7-MSP	42.42	9.67	53.25	11.15	10.84	8.06	0.001*

M: mean

SD: standard deviation

MD: mean difference

P: probability level which is significant at $P \leq 0.05$

[figure not shown]

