Figure (73): Bar chart showing mean of pretreatment, post treatment records and difference between them regarding anteroposterior linear dental measurements in group II.

- **Comparison between both groups:**

Comparison between group I & II regarding difference between pretreatment & posttreatment records of anteroposterior - linear dental measurements was performed by using Mann Whitney test which revealed insignificant difference between them regarding all measurements except U1-tip/S Ver (Group I was significantly lower than group II) as $P <0.05$, as presented in table (32) and figure (74).

Table (32): Comparison between both groups regarding anteroposterior - linear dental measurements:

[figure not shown]
Difference Anteroposterior Linear Dental Measurements	Group I		Group II		P value
	MD	SD	MD	SD	
U1-tip/S Ver	0.02	0.47	0.59	0.13	0.002*
U1-apex/ S Ver	-0.02	1.21	0.43	0.08	0.28
L1-tip/S Ver	-1.16	2.50	-0.54	1.61	1
U4-tip/S Ver	1.06	1.17	1.11	1.76	0.97
U4-apex/S Ver	2.59	1.64	1.79	1.19	0.31
U5-tip/S Ver	1.40	1.00	1.88	1.49	0.71
U5-apex/S Ver	1.86	1.55	1.37	1.58	0.71
MBc6/S Ver	-3.78	1.31	-4.51	3.39	0.8
U6-apex/S Ver	-2.78	1.64	-2.12	2.52	1
MBc7/S Ver	-3.26	1.55	-5.32	3.62	0.12
U7-apex/S Ver	-2.50	2.45	-2.40	0.98	0.86
overjet	1.19	2.43	0.85	1.25	0.75

SD: standard deviation

MD: mean difference

P: probability level which is significant at $P \leq 0.05$

Figure (74): Bar chart showing comparison between both groups regarding anteroposterior linear dental measurements.

b. Vertical

- Group I:**

In group I pretreatment records, post treatment records and difference between them regarding vertical- linear- dental measurements were presented in table (33) and figure (75).

Comparison between pretreatment & post treatment records was performed by using Paired t-test which revealed significant difference between them in all measurements as $P < 0.05$ except overbite as there was insignificant difference between pre & post as $P > 0.05$. In U1-tip/PP, pre was significantly lower than post, while in U4-tip/PP, U5-tip/PP, MBc6/PP, MBc7/PP and L1-tip/PP pre was significantly higher than post as $P < 0.05$, as presented in table (33).

Table (33): Mean & standard deviation of pretreatment, post treatment records and difference between them regarding vertical - linear dental measurements in group I:

Group I Vertical Linear Dental Measurements	Pre		Post		Difference		P value
	M	SD	M	SD	MD	SD	
U1-tip/PP	27.68	3.67	27.86	3.67	0.18	0.52	0.005*

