U4-tip/PP	25.79	3.18	25.10	3.00	-0.69	0.56	0.001*
U5-tip/PP	25.25	2.82	24.56	3.01	-0.70	0.63	0.001*
MBc6/PP	23.90	2.50	22.75	2.75	-1.15	0.88	0.003*
MBc7/PP	21.43	2.81	20.77	3.24	-0.65	0.91	0.001*
L1-tip/PP	24.45	3.73	23.63	5.55	-0.82	2.67	0.008*
overbite	3.23	1.14	4.23	2.57	1.00	2.68	0.119

M: mean

SD: standard deviation

MD: mean difference

P: probability level which is significant at $P \leq 0.05$

[figure not shown]

Figure (75): Bar chart showing mean of pretreatment, post treatment records and difference between them regarding vertical linear dental measurements in group I.

- **Group II:**

In group II pretreatment records, post treatment records and difference between them regarding vertical- linear- dental measurements were presented in table (34) and figure (76).

Comparison between pretreatment & post treatment records was performed by using Paired t-test which revealed insignificant difference between them in all measurements as $P > 0.05$ except U4-tip/PP, MBc6/PP & MBc7/PP as Pre was significantly higher than post as $P < 0.05$., as presented in table (34).

Table (34): Mean & standard deviation of pretreatment, post treatment records and difference between them regarding vertical - linear dental measurements in group II:

Group II Vertical Linear Dental Measurements	pre		post		Difference		P value
	M	SD	M	SD	M	SD	
U1-tip/PP	27.78	3.27	28.05	3.19	0.27	-0.09	0.16
U4-tip/PP	25.98	2.93	25.25	3.13	-0.73	0.86	0.036*
U5-tip/PP	25.21	3.05	24.76	3.62	-0.45	1.36	0.352
MBc6/PP	24.00	3.28	22.47	3.13	-1.53	1.21	0.005*
MBc7/PP	22.00	3.65	20.11	3.72	-1.88	1.83	0.015*
L1-tip/PP	24.74	4.08	24.18	4.37	-0.56	1.79	0.374
overbite	3.56	2.61	4.67	2.43	1.11	1.47	0.053

M: mean

SD: standard deviation

MD: mean difference

P: probability level which is significant at $P \leq 0.05$

[figure not shown]

Figure (76): Bar chart showing mean of pretreatment, post treatment records and difference between them regarding vertical linear dental measurements in group II.

- **Comparison between both groups:**

Comparison between group I & II regarding difference between pretreatment & posttreatment records of vertical - linear dental measurements was performed by using Mann Whitney test which revealed insignificant difference between them regarding all measurements, as presented in table (35) and figure (77).

Table (35): Comparison between both groups regarding vertical - linear dental measurements:

Difference Vertical Linear Dental Measurements	Group I		Group II		P value

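### Six between-group P values labelled Mann-Whitney appear to be pooled t-tests on printed summaries with faulty Group II SDs, so the only significant result in Table 32 (U1-tip/S Ver, 0.002) is unverified

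*SAP*

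**What the plan says.** Under Tests used, the SAP states "Comparisons 2 different groups was performed by using Mann Whitney test". The independent t-test has a narrower role: "Comparison between quantitative continuous data (Age & Duration) was performed by Independent t-test". Table 11 reports the changes as non-normal in both groups, which explains the choice of a rank test.

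The text above each comparison table repeats the label: "records of vertical skeletal measurements was performed by using Mann Whitney test" (Table 20), "records of anteroposterior angular dental measurements was performed by using Mann Whitney test" (Table 23) and "records of vertical - linear dental measurements was performed by using Mann Whitney test" (Table 35). The text above Table 32 also names Mann-Whitney and reports no significant difference for "all measurements except U1-tip/S Ver (Group I was significantly lower than group II". The P in that row is 0.002, the smallest of the five significant between-group results in the SAP. The other four are U6-FHP 0.03, U5-MSP 0.009, U6 crown inclination 0.04 and transverse U5 0.04.

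**The concern.** A rank test uses the ordering of the patients' changes and takes no SD as input. If a P labelled Mann-Whitney can be recovered from a printed mean and SD, and that SD is not an SD of change, the P was evidently worked out from the summary table and carries the table's error with it.

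At stake is one stated significant difference between the randomised groups, on upper incisor position. A reader told that a rank test gave 0.002 would think it immune to a wrong SD column, so correcting the SDs alone would leave the claim standing.

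**Working it through.** **Inputs.** Group sizes come from Table 13: "Group I 2 16.67% 10 83.33% 0.001" gives 2 + 10 = 12, and "Group II 3 33.33% 6 66.67% 0.13" gives 3 + 6 = 9. Change means and SDs come from Tables 20, 23, 32 and 35. Group II pre and post SDs come from Tables 19, 22, 31 and 34.

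**Step 1: reproduce the printed P.** Pooled variance is sp² = (11·s₁² + 8·s₂²)/19, and t = (M₁ − M₂)/(sp·√(1/12 + 1/9)) on 19 df, two-sided. For U1-tip/S Ver:

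- sp² = (11 × 0.47² + 8 × 0.13²)/19 = (2.430 + 0.135)/19 = 0.135, so sp = 0.367
- SE = 0.367 × 0.441 = 0.162
- t = (0.02 − 0.59)/0.162 = −3.52, P = 0.0023 (printed 0.002)

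**Step 2: all six rows, with the source of the Group II SD.**

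| Row (table) | Group I mean (SD) | Group II mean (SD) | Printed P | Pooled t | Welch | Group II post SD − pre SD |
|---|---|---|---|---|---|---|
| PP-SN (20) | 0.31 (0.91) | 0.17 (0.27) | 0.66 | 0.662 | 0.622 | 3.31 − 3.58 = −0.27 |
| U1-NA (23) | 0.44 (1.88) | 0.18 (0.85) | 0.70 | 0.705 | 0.677 | 5.79 − 4.94 = 0.85 |
| U1-FHP (23) | 0.97 (1.46) | 0.43 (0.83) | 0.33 | 0.334 | 0.298 | 4.83 − 4.00 = 0.83 |
| U1-tip/S Ver (32) | 0.02 (0.47) | 0.59 (0.13) | 0.002 | 0.0023 | 0.0015 | 2.99 − 2.86 = 0.13 |
| U1-apex/S Ver (32) | −0.02 (1.21) | 0.43 (0.08) | 0.28 | 0.282 | 0.225 | 3.18 − 3.09 = 0.09 |
| U1-tip/PP (35) | 0.18 (0.52) | 0.27 (−0.09) | 0.61 | 0.616 | 0.568 | 3.19 − 3.27 = −0.08 |

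Five rows match to printed precision. U1-tip/PP needs 0.09 in place of the impossible −0.09. It then matches 0.61 only by truncation, or within the range that input rounding allows (0.573 to 0.659). Welch does not reproduce the set. Sizes of 10 and 10, as the protocol's 20 patients might suggest, fit less well (PP-SN 0.647, U1-apex/S Ver 0.256).

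**Step 3: the other 42 between-group rows.** Only A-NV in Table 17 agrees as closely (0.2397 against 0.24). Its SDs are not differences of SDs, so coincidence is likely. Others are far off: overbite 0.91 against 0.27, U4-FHP 0.15 against 0.82. Two more Group II rows carry a post-minus-pre SD: U7-FHP (9.62 − 8.81 = 0.81) and U7-MSP (13.42 − 6.55 = 6.87). Their P values do not match a t-test (0.23 against 0.16; 0.0002 against 0.06). The SD error and the t-test pattern therefore overlap in these six rows but are not the same fault.

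**Step 4: U1-tip/S Ver against its own paired test.** Table 31 prints a Group II change of 0.59 (SD 0.13) with paired P 0.12.

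- From the printed SD: t = 0.59 × √9/0.13 = 13.6 on 8 df, P about 8 × 10⁻⁷
- From the printed P: t = 1.740, so SD = 0.59 × 3/1.740 = 1.02

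The two printed figures cannot both be right.

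**Step 5: illustration, assuming the paired P of 0.12 is right.**

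- sp² = (11 × 0.47² + 8 × 1.02²)/19 = (2.430 + 8.323)/19 = 0.566, so SE = 0.752 × 0.441 = 0.332
- t = −0.57/0.332 = −1.72, P = 0.10 (Welch 0.15)

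This is not the Mann-Whitney P, which cannot be computed from the documents. Treated in the same way, the other five rows stay non-significant (P 0.37 to 0.72).

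**The case against.** The main objection is that changing the test is not what moves the result. Normal samples fixed to the printed U1-tip/S Ver summaries give a median exact Mann-Whitney P of about 0.002, so the rank test would also be significant if 0.13 were a real SD. This stands. A reader might infer that the t-test by itself created the significance; it did not. The doubt comes from the SD of 0.13, and the apparent t-test is how that figure reached the between-group comparison.

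A reader might also infer that the significant between-group results fall from five to four. The documents do not establish that. The SAP calls the changes non-normal. With both groups negatively skewed (an assumed lognormal shape) and SDs of 0.47 and 1.02, Mann-Whitney reaches 0.05 in about 55% of simulated samples. The SD of 1.02 also rests on one printed paired P, and paired P values in nearby incisor rows are unreliable: Table 30 prints 78.77 as the P for Group I U1-tip/S Ver, and Table 33 prints 0.005 for Group I U1-tip/PP where its summaries give about 0.26.

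A third tempting argument is that some of the printed P values cannot arise from an exact Mann-Whitney test on 12 and 9 patients without ties. It does not discriminate: 16 of the other 42 rows fail the same check, 0.002 passes it, and ties or software settings are not excluded.

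The six rows were also grouped after their match was seen, so no formal probability should be attached to it. Nor are they all the anchorage-loss measures: overjet, lower incisor and premolar rows are unaffected. What survives is that the printed P values follow from Group II figures that are not SDs of change, one of them negative.

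**Conclusion.** The point holds as an inference from reproduction, which patient-level data would settle. Six of 48 between-group P values appear to be pooled t-tests on printed summaries, not the stated rank test, and they inherit faulty Group II SDs. One stated conclusion is affected: the U1-tip/S Ver difference, the only significant row in Table 32, is unverified. The illustrative t-test P of 0.10 (Welch 0.15) assumes that the Group II paired P of 0.12, n = 9 and the printed means are right. The documents support neither that the difference is real nor that it is absent. The other five rows are reported as non-significant and remain so in the illustration.

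**What to change.** Re-run the stated Mann-Whitney test from patient-level changes for the six rows. At the same time recompute the Group II SDs of change, and replace the P values in Tables 20, 23, 32 and 35 and the SDs there and in the matching within-group tables (19, 22, 31 and 34). Until that is done, do not list U1-tip/S Ver as a significant difference. If the patient-level values no longer exist, label the six rows as summary-based t-tests and withdraw the U1-tip/S Ver claim.

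The cost is six tests and six SDs on existing data. The report may lose its only significant linear anteroposterior difference between groups.

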	MD	SD	MD	SD	
U1-tip/PP	0.18	0.52	0.27	-0.09	0.61
U4-tip/PP	-0.69	0.56	-0.73	0.86	0.81
U5-tip/PP	-0.70	0.63	-0.45	1.36	0.86
MBc6/PP	-1.15	0.88	-1.53	1.21	0.81
MBc7/PP	-0.65	0.91	-1.88	1.83	0.11
L1-tip/PP	-0.82	2.67	-0.56	1.79	0.65
overbite	1.00	2.68	1.11	1.47	0.27

SD: standard deviation

MD: mean difference

P: probability level which is significant at $P \leq 0.05$

[figure not shown]

Figure (77): Bar chart showing comparison between both groups regarding vertical linear dental measurements

c. Transverse

- **Group I:**

In group I pretreatment records, post treatment records and difference between them regarding transverse- linear- dental measurements were presented in table (36) and figure (78).

Comparison between pretreatment & post treatment records was performed by using Paired t-test which revealed significant difference between them in all measurements as $P < 0.05$ except U4 as there was insignificant difference between pre & post as $P > 0.05$. In U5, there was a statistically significant difference as $P < 0.05$ (pre was significantly lower than post), while in U6 and U7 there was a highly statistical significant difference as $P < 0.001$ (pre was significantly lower than post), as presented in table (36).

Table (36): Mean & standard deviation of pretreatment, post treatment records and difference between them regarding transverse - linear dental measurements in group I:

Group I Transverse Linear Dental Measurements	Pre		Post		Difference		P value
	M	SD	M	SD	MD	SD	
U4	16.80	2.01	18.55	2.03	1.75	1.36	0.438
U5	18.83	2.06	20.84	1.94	2.01	1.11	0.001*
U6	21.96	2.21	23.39	2.06	1.43	0.98	0.000**
U7	24.50	2.55	25.45	2.50	0.95	1.01	0.000**

M: mean

SD: standard deviation

MD: mean difference

P: probability level which is significant at $P \leq 0.05$

[figure not shown]

Figure (78): Bar chart showing mean of pretreatment, post treatment records and difference between them regarding transverse - linear dental measurements in group I.

- **Group II:**

In group II pretreatment records, post treatment records and difference between them regarding transverse- linear- dental measurements were presented in table (37) and figure (79).

Comparison between pretreatment & post treatment records was performed by using Paired t-test which revealed insignificant difference between them in all measurements as $P < 0.05$, as presented in table (37).

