Table (37): Mean & standard deviation of pretreatment, post treatment records and difference between them regarding transverse - linear dental measurements in group II:

Group II Transverse Linear Dental Measurements	pre		post		Difference		P value
	M	SD	M	SD	M	SD	
U4	17.45	2.12	18.04	2.02	0.60	1.95	0.387
U5	20.04	1.82	20.80	2.00	0.76	1.59	0.188
U6	23.01	1.76	23.66	1.35	0.65	1.15	0.130
U7	25.04	2.14	25.06	1.80	0.02	2.30	0.984

M: mean

SD: standard deviation

MD: mean difference

P: probability level which is significant at $P \leq 0.05$

[figure not shown]

Figure (79): Bar chart showing mean of pretreatment, post treatment records and difference between them regarding transverse - linear dental measurements in group II.

- **Comparison between both groups:**

Comparison between group I & II regarding difference between pretreatment & posttreatment records of transverse – linear dental measurements was performed by using Mann Whitney test which revealed insignificant difference between them regarding all measurements except U5 (Group I was significantly higher than group II) as $P < 0.05$, as presented in table (38) and figure (80).

Table (38): Comparison between both groups regarding transverse - linear dental measurements:

Difference Transverse Linear Dental Measurements	Group I		Group II		P value
	MD	SD	MD	SD	
U4	1.75	1.36	0.60	1.95	0.19
U5	2.01	1.11	0.76	1.59	0.04*
U6	1.43	0.98	0.65	1.15	0.09
U7	0.95	1.01	0.02	2.30	0.31

SD: standard deviation

MD: mean difference

P: probability level which is significant at $P \leq 0.05$

[figure not shown]

Figure (80): Bar chart showing comparison between both groups regarding transverse -linear dental measurements.

C. Soft tissue

- **Group I:**

In group I pretreatment records, post treatment records and difference between them regarding soft tissue measurements were presented in table (39) and figure (81,82).

Comparison between pretreatment & post treatment records was performed by using Paired t-test which revealed insignificant difference between them in all measurements as $P > 0.05$, as presented in table (39).

Table (39): Mean & standard deviation of pretreatment, post treatment records and difference between them regarding soft tissue measurements in group I:

Group I Soft tissue Measurements	Pre		Post		Difference		P value
	M	SD	M	SD	MD	SD	
Ls/E-line distance	2.72	1.27	2.81	0.74	0.10	0.70	0.643
Li/E-line distance	2.40	1.58	2.05	1.46	-0.36	0.96	0.226
NLA angle	97.44	12.44	98.61	13.17	1.17	3.37	0.253

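### Most Group I paired-test P values in SAP Tables 30, 33 and 36 do not follow from their own rows; the significant result for L1-tip/PP is impossible, and three other conclusions reverse if the printed difference SDs are right

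*SAP*

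**What the plan says.** The SAP's list of tests assigns the paired t-test to pre/post comparisons, and the table footnotes set significance at 0.05. The Group I results at issue are under III.B.2, Linear dental measurements.

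- **Vertical (Table 33).** Every row except overbite is called significant. For the upper incisor: "In U1-tip/PP, pre was significantly lower than post", with the row "U1-tip/PP 27.68 3.67 27.86 3.67 0.18 0.52 0.005". For the lower incisor: "L1-tip/PP pre was significantly higher than post as $P < 0.05", with the row "L1-tip/PP 24.45 3.73 23.63 5.55 -0.82 2.67 0.008". The columns are pre mean and SD, post mean and SD, difference mean and SD, and P.
- **Transverse (Table 36).** The text reports "significant difference between them in all measurements as $P < 0.05$ except U4 as there was insignificant difference between pre & post". The row is "U4 16.80 2.01 18.55 2.03 1.75 1.36 0.438". Table 38 repeats the same Group I difference and SD: "U4 1.75 1.36 0.60 1.95 0.19". The text adds "while in U6 and U7 there was a highly statistical significant difference as $P < 0.001".
- **Anteroposterior (Table 30).** U4-tip/S Ver (difference 1.06, SD 1.17, P 0.124) is not among the listed significant rows. U5-tip, U6-apex, MBc7 and U7-apex are described as P below 0.0001. The P value printed for U1-tip/S Ver is 78.77.

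**The concern.** A paired t-test P value is fixed by the mean difference, the SD of the differences and n, so each row can be checked from what is printed. In these three tables most rows fail that check, and the text follows the printed P values. Readers are told that L1-tip/PP changed significantly, which its SDs rule out. They are also told that U1-tip/PP changed and that transverse U4 and U4-tip/S Ver did not, which the printed difference SDs contradict. These are incisor and first-premolar measurements, so they bear on how anchorage loss in Group I is described.

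**Working it through.** **Inputs.** Group I n = 12 (Table 13: 2 male, 10 female), so df = 11. Means and SDs are as printed in Tables 15, 18, 30, 33 and 36. The SAP does not state sidedness; two-sided is assumed.

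**Formulas.**
- t = MD / (SD/√12), √12 = 3.464; P = 2·Pr(T₁₁ > |t|). MD and SD were each varied by ±0.005 for rounding.
- For any pre-post correlation, the difference SD lies between |s₁ − s₂| and s₁ + s₂.
- Difference SD at which P = 0.05: |MD| × 3.464 / 2.201.
- Correlation implied by a difference SD: r = (s₁² + s₂² − SD²) / (2·s₁·s₂).

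**Does the method reproduce the SAP elsewhere?** Yes. In the other Group I tables (15, 18, 21, 24, 27, 39), 22 of 25 rows reproduce at n = 12, against 4 at n = 10, 7 at n = 11, 4 at n = 13 and 2 at n = 24. For Group II at n = 9, all 20 rows checked in Tables 31, 34 and 37 reproduce (three U1 rows with unusable printed SDs were left out).

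**Count in Tables 30, 33 and 36.** Printed P values outside the rounding range: 9 of 12, 6 of 7 and 3 of 4, so 18 of 23. Allowing for truncated P values rescues U5-apex/S Ver (0.0016, printed 0.001), which leaves 17. Transverse U5 (0.00006, printed 0.001) is a trivial mismatch; without it, 16.

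**L1-tip/PP.**
- Printed SD: t = −0.82 / (2.67/3.464) = −1.06, P = 0.310 (printed 0.008).
- SD needed for P < 0.05: 0.82 × 3.464 / 2.201 = 1.29, which would imply a correlation of 1.04.
- Smallest possible SD: 5.55 − 3.73 = 1.82, giving t = −1.56 and P = 0.147 (0.143 with rounding).

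**The four conclusions that change at 0.05.**

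| Row | MD (SD) | Printed P | t | Recomputed P | SD at P = 0.05 | Feasible SD |
|---|---|---|---|---|---|---|
| L1-tip/PP | −0.82 (2.67) | 0.008 | −1.06 | 0.310 | 1.29 | 1.82 to 9.28 |
| U1-tip/PP | 0.18 (0.52) | 0.005 | 1.20 | 0.256 | 0.28 | 0 to 7.34 |
| U4-tip/S Ver | 1.06 (1.17) | 0.124 | 3.14 | 0.009 | 1.67 | 0.17 to 7.71 |
| U4 transverse | 1.75 (1.36) | 0.438 | 4.46 | 0.001 | 2.75 | 0.02 to 4.04 |

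Only L1-tip/PP has its threshold outside the feasible range. The other three stated conclusions could stand only with a different difference SD. Transverse U4 would need a correlation below 0.07, against 0.77 implied by its printed SD and 0.85 to 0.92 in the other transverse rows. Its printed 0.438 is still unattainable: at the largest feasible SD, 4.04, P is about 0.16. The printed difference SDs recur unchanged in Tables 32, 35 and 38.

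**Impossible values that change no conclusion.** 78.77 for U1-tip/S Ver is that row's pre-treatment mean (recomputed P 0.885). L1-tip/S Ver is printed 0.948; the maximum is 0.648 and the recomputed value 0.136.

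**Labels.** Of the four rows called P below 0.0001, MBc7/S Ver qualifies (0.00002); U5-tip (0.0005), U6-apex (0.00011) and U7-apex (0.0047) do not. Transverse U7, called P below 0.001, gives 0.008.

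**Tables 15 and 18.** SNA is printed 0.854 (recomputed 0.893), PP-SN 0.425 (0.263) and MP-SN 0.265 (0.412). Each of the last two printed values fits the other's row. No conclusion changes.

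**The case against.** **The likely fault is misplaced P values, not wrong SDs.** In Tables 30, 33 and 36, 15 of the 20 printed P values that have a row above them fit that row. Examples in Table 30 are 0.861 (fits U1-tip), 0.948 (fits U1-apex) and 0.010 (fits U4-tip). Some matches are weak because 0.000 or 0.001 fits many rows. The inference is reasonable but needs the raw output. If right, it supports the reversals and puts P-value alignment first among the checks.

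**The trial is about molars.** None of the four altered conclusions concerns a molar. Every Group I molar conclusion at 0.05 in these tables survives, and all affected tests lie within one arm. This stands, and it limits the reach of the error. It does not make the four statements correct.

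**The impossibility depends on n.** The measurement tables print no n. If both sides were counted (n = 24), the smallest P for L1-tip/PP would be about 0.038 (0.036 with rounding). Significance would then be attainable, though 0.008 would not, and the printed SD would give 0.146. With only 2 of 25 control rows reproducing at n = 24, against 22 at n = 12, this is not a credible way out.

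**Some label points are small.** A printed 0.000 is compatible with U5-tip and U6-apex, and the SAP elsewhere words the same entry as P below 0.001, which both meet. For those two rows only the wording is wrong. U7-apex and transverse U7 are substantive label errors.

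**Conclusion.** The concern holds, and the Group I linear results should not be relied on as printed. At least 17 of 23 P values disagree with their own rows. The significant result for L1-tip/PP is ruled out given n = 12 and the printed pre and post SDs. The reversals for U1-tip/PP, U4-tip/S Ver and transverse U4 rest additionally on the printed difference SDs.

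The other four significance claims in the Table 33 text (U4-tip, U5-tip, MBc6, MBc7) remain correct at 0.05. Forward movement of U4-apex, U5-tip and U5-apex is already reported as significant, so the anchorage-loss picture is altered in part, not overturned. Nothing here shows an error in the between-group results of Tables 32, 35 and 38.

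**What to change.** 1. Re-run from the raw data the 23 Group I paired t-tests in Tables 30, 33 and 36, plus SNA (Table 15) and PP-SN and MP-SN (Table 18).
2. Compare the printed P columns with the software output row by row, looking first for a shift of one row, and check each difference SD. If an SD changes, carry the change into Tables 32, 35 and 38.
3. Print each P value against its own variable, replace 78.77, and state n in each table.
4. Rewrite the three Group I paragraphs (anteroposterior, vertical, transverse) and the P < 0.0001 and P < 0.001 labels from the re-run results.

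The cost is 26 existing tests, an SD check, and edits to tables and text. No new data are needed.
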